### **1. Scientific Background.**

Contrast-induced nephropathy (CIN) is a frequent cause of acute kidney injury (AKI), particularly among hospitalized patients with diabetes mellitus. Individuals with diabetes are especially vulnerable due to metabolic disturbances, oxidative stress, and endothelial dysfunction, which heighten the risk of CIN following contrast exposure. Mechanistically, CIN is driven by reactive oxygen species (ROS), impaired nitric oxide (NO) bioavailability, and inflammatory processes (Tumlin et al., 2002; Heyman et al., 2008).

Remote ischemic preconditioning (RIPC)—a procedure involving brief episodes of non-lethal ischemia and reperfusion applied to a limb—has emerged as a potential non-invasive strategy to mitigate ischemia-reperfusion injury. Preclinical and clinical studies suggest that RIPC activates endogenous protective pathways, including the induction of heme oxygenase-1 (HO-1), modulation of NO signaling, activation of K+-ATP channels, and reduction of systemic inflammation (Zarbock et al., 2015; Er et al., 2012).

However, the efficacy of RIPC in diabetic populations remains controversial. Experimental data indicate that diabetes may interfere with key molecular signaling pathways responsible for RIPC-mediated protection. Impaired humoral signaling, autonomic dysfunction, increased oxidative stress, and diabetic neuropathy have all been implicated as potential mechanisms of attenuation (Li et al., 2010; Hausenloy et al., 2013). Approximately 20–50% of individuals with diabetes mellitus develop peripheral neuropathy, which may compromise neurogenic components of RIPC signaling (Pop-Busui et al., 2017).

Despite these concerns, some clinical trials have reported preserved protective responses in diabetic patients, particularly in the context of contrast administration. For instance, the RenPro Trial found that RIPC significantly reduced the incidence of CIN in both diabetic and non-diabetic populations (Er et al., 2012). These contradictory results may

reflect differences in glycemic control, duration of diabetes, antidiabetic pharmacotherapy, and the presence of comorbidities.

Although early evidence pointed toward a protective effect of RIPC in preventing CIN, especially via activation of cytoprotective pathways, growing data suggests that such benefits may be attenuated in diabetic populations due to disease-related metabolic and neurovascular alterations. The present study was initially designed to test the protective efficacy of RIPC, while also specifically addressing the possibility that these mechanisms might be disrupted in patients with diabetes mellitus. This dual focus reflects the urgent need to clarify the clinical utility of RIPC in this high-risk population.

## 2. Objectives

### Primary Objective

- To evaluate the impact of RIPC on the incidence of CIN in diabetic patients undergoing coronary catheterization, using serum creatinine, as biomarkers.

### Secondary Objectives

- To assess HO-1 levels and other oxidative stress markers (malondialdehyde (MDA) before and after RIPC.
- To identify predictors of RIPC failure.
- To evaluate ICU/hospital stay duration, clinical status and survival at discharge.

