## 7.4 Multivariate Analysis

- **Binary logistic regression** to predict CIN occurrence, adjusted for covariates.

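### Does the secondary objective on predictors of RIPC failure need its own definition and interaction analysis in the plan?

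*Combined protocol and SAP*

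**What the plan says.** The Secondary Objectives in Section 2 include "To identify predictors of RIPC failure". The phrase occurs nowhere else: Section 6 has no endpoint that measures it, and no item of Section 7 is assigned to it.

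The nearest analysis is the binary logistic regression in 7.4, whose purpose is "to predict CIN occurrence, adjusted for covariates". It lists no covariates and no interaction, and does not say whether one or both arms enter. The repeated-measures ANOVA in 7.3 could bear on biomarker response. The objective listed just before this one concerns HO-1 and "other oxidative stress markers (malondialdehyde (MDA) before and after RIPC".

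Section 1 explains the interest. It says that "such benefits may be attenuated in diabetic populations due to disease-related metabolic and neurovascular alterations" and describes the study as "specifically addressing the possibility that these mechanisms might be disrupted in patients with diabetes mellitus". It lists several diabetes-related processes that "have all been implicated as potential mechanisms of attenuation", and suggests that conflicting trial results may reflect "differences in glycemic control, duration of diabetes, antidiabetic pharmacotherapy, and the presence of comorbidities". Section 4 excludes patients without diabetes.

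**The concern.** Section 1 gives the trial two aims: to test whether RIPC works, and to ask whether diabetes blunts it. With no non-diabetic patients, blunting of the effect on CIN can be studied only through factors that vary among diabetics, and this objective looks like the place for it. Yet the only multivariable model has CIN as its outcome, and CIN also occurs in controls, who have no RIPC to fail.

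A factor that raises CIN risk equally in both arms would then appear as a predictor. Reported under this objective, it would be read as a reason why RIPC fails in diabetes, although RIPC worked equally well with and without it. That would be a wrong conclusion on half of the trial's stated focus.

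**Working it through.** The documents attach no event rate, effect size or power to this objective, so there is no planned figure to reproduce. All rates, odds ratios and arm sizes below are assumptions, apart from the total of 71 (Sections 3 and 9). The factor prevalence of 20%-50% borrows the neuropathy figure in Section 1, "Approximately 20–50% of individuals with diabetes mellitus develop peripheral neuropathy, which may compromise neurogenic components of RIPC signaling", which is not trial data.

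**1. What failure could mean.** Three readings fit the text:
- CIN despite RIPC. A model of CIN in the RIPC arm answers this as defined.
- A smaller RIPC effect on CIN. This needs an arm-by-factor interaction.
- No HO-1 or MDA response. 7.3 could address this against controls.

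Section 1 speaks both of attenuated benefit and of disrupted mechanisms, so it does not settle the choice.

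**2. Can the RIPC arm alone separate a modifier from a risk factor?** Take 20% CIN in controls without the factor, odds 0.20/0.80 = 0.25.
- Modifier: no effect in controls; RIPC OR 1/3 without the factor and 1 with it. Controls 20% and 20%. RIPC without the factor: odds 0.25/3 = 0.083, or 7.7%; with it, 20%.
- Pure risk factor: OR 3 in both arms, RIPC OR 1/3 throughout. Controls with the factor: odds 0.75, or 43%. RIPC without it 7.7%; with it, odds 0.75/3 = 0.25, or 20%.

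The RIPC arm shows 7.7% and 20% in both cases. Only the controls differ.

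**3. Can a main-effects model separate them?** For the same kind of modifier, with 36 RIPC and 35 control patients, control CIN 10%-30% and prevalence 20%-50%, a logistic fit to the expected counts without an interaction gives RIPC OR 0.442-0.654 and factor OR 1.540-1.624. A pure risk factor given those constant odds ratios yields the same coefficients. In simulation at N = 71 (20,000 trials per setting) the factor is flagged in 6.0%-14.4% of trials as a modifier and in 6.3%-14.4% as a pure risk factor, never more than 0.6 points apart.

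**4. What would an interaction test give?** Approximate Wald power is Φ(ln(ROR)/√Σ[1/(n·p·(1−p))] − 1.96), summed over the four arm-by-factor cells, where ROR is the ratio of odds ratios. With 35.5 patients per arm, 20% CIN, 50% prevalence and ROR 3, each cell has 17.75 patients. Three cells have p = 0.20 and one has p = 0.077, so the sum is 1.85. Then 1.099/1.360 − 1.96 = −1.15, which gives 12.5%. Over control CIN 20%-40%, prevalence 20%-50% and ROR 3 or 5, power is about 10%-30%.

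A Firth-penalised interaction test, simulated over control CIN 10%-30% and prevalence 20%-50% (RIPC OR 0.33 or 0.6 without the factor; factor OR 1 or 2 in controls), gives:

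| ROR | Power |
|---|---|
| 3 | 2.3%-17.0% |
| 5 | 5.5%-32.8% |
| 10 | 14.6%-57.3% |

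The median ratio of upper to lower 95% limit is 69 at best; in that setting the median limits are 0.36 and 24.6. At ROR 3, 2.7%-84.7% of trials have at least one cell without an event, where ordinary maximum likelihood breaks down.

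**5. Is the analysis simple to run?** Take invented CIN counts without and with the factor: controls 4/23 and 5/12, RIPC 0/24 and 3/12. Adding 0.5 to each event and non-event count gives [(3.5/9.5)/(0.5/24.5)] ÷ [(5.5/7.5)/(4.5/19.5)] = 18.05/3.18 = 5.68, which equals the Firth estimate. The intervals do not agree: Wald limits from the adjusted counts are 0.19-171, and the penalised profile limits are 0.30-916. The shortcut also serves only yes/no factors, whereas glycaemic control and diabetes duration are naturally continuous.

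**The case for a change.** The best case for a change is that the gap is real and cheap to close. An undefined objective lets any covariate with p < 0.05 be published as a reason why RIPC fails, and one sentence would prevent that. Section 9 shows that data collection had ended and preliminary primary results had been seen, so the choice of meaning is open to hindsight.

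The absence of a definition stands, and so does the warning that neither 7.4 nor a RIPC-arm fit identifies modifiers of the RIPC effect. The rest is weaker. The harm requires a misreport that the plan does not announce. The identical coefficients in step 3 follow from how the pair was matched, and they do not show how often a strong risk factor would be mislabelled. If failure means CIN despite RIPC, the RIPC-arm model is the right one, so a blanket ban on that label goes too far. The interaction analysis suits only one of three readings, and it needs factors that the documents do not say were recorded.

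**Conclusion.** No change to the plan. The objective is loosely worded and has no linked analysis, but this is missing detail in a secondary objective. No stated method is wrong: 7.4 is correctly described as a model of CIN, and an analyst can report its results under that name. Whoever writes the report should say which meaning of failure is used and should not read CIN predictors as modifiers of the RIPC effect. That is ordinary care in reporting.

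The one substantive addition, an interaction analysis, would have 2.3%-17.0% power at a ratio of odds ratios of 3 and at best a 69-fold interval, so it could not tell blunting from its absence. These figures rest on the assumed rates above and a near 1:1 split of 71 patients. The textual conclusion needs none of them, and the primary comparison is unaffected.

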## 3. Study Design

- **Type:** Randomized, parallel-group clinical trial.
- **Setting:** ICU, Hospital General Universitario Santa Lucía, Cartagena (Murcia, Spain)
- **Randomization method:** Based on sealed envelopes, using block randomization into two groups: **RIPC** and non- **RIPC**.
- **Groups:**
  - **Intervention Group:** RIPC + hydration.
  - **Control Group:** Hydration only.
- **Planned sample Size:** The sample size was determined based on data from the ARIAM registry, a Spanish national database focused on patients with acute coronary syndrome (ACS) admitted to intensive care units. According to ARIAM estimates, approximately 35–40 patients per year would meet the eligibility criteria for recruitment. It was therefore decided that the sample size would be defined by the number of patients admitted to our department with the specified characteristics during a fixed time period, establishing a convenience sampling strategy over a two-year period.
- **Actual enrolled patients:** 71.
- **Analysis population:** Both Intention-to-Treat (ITT) and Per Protocol (PP).

## 4. Eligibility Criteria

### **Inclusion**

- Adults aged  $\geq 18$  years with diabetes mellitus.
- Hospitalized for acute coronary syndrome and scheduled for coronary angiography.

### **Exclusion**

- Non-diabetic.
- Pregnant or lactating.
- Kidney transplant recipients.
- Recent exposure to contrast agents.
- End-stage renal disease.
- Participation in other clinical trials.

## 5. Intervention

**RIPC Procedure:** Four cycles of 5-minute ischemia (inflation of a blood pressure cuff to 50 mmHg above systolic BP) followed by 5-minute reperfusion. The procedure was performed within 45 minutes prior to catheterization.

**Contrast Agent:** Visipaque® (low-osmolar)

## 6. Outcome Measures

### **Primary Endpoint**

- CIN defined as either a 25% increase in serum creatinine (SCr) from baseline or a 0.5 mg/dL increase in absolute SCr value—within 72 hours after intravenous contrast administration.

### **Secondary Endpoints**

- Plasma, urinary, and intracellular HO-1 levels.
- Oxidative stress markers (MDA).
- Cardiac stress biomarkers (NT-proBNP).
- Inflammatory and hematological indices: C-reactive protein (CRP), Total leukocyte count, Neutrophil and lymphocyte counts Neutrophil-to-lymphocyte ratio (NLR).
- Duration of ICU/hospital stay duration
- Mortality, readmission, clinical status and need for dialysis.

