## 7. Statistical Analysis Plan (SAP)

### **7.1 Descriptive Statistics**

- **Qualitative variables:** Presented as frequencies and percentages per group/subgroup.
- **Quantitative variables:** Described using minimum, maximum, mean, and standard deviation.

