## 7.2 Univariate Analysis

- **Qualitative comparisons:** Chi-square test.
- **Quantitative comparisons:** Student's T-test, after verifying:
  - **Normality:** Shapiro-Wilk test.
  - **Homogeneity of variances:** Levene test.
- If assumptions are violated: Mann-Whitney U test will be used.

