## 7.6 Missing Data

- $\leq 5\%$  Complete case.
- $\geq 5\%$ : Multiple imputation considered
- Sensitivity analysis may be performed

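### The plan has no rule for in-hospital deaths in the ICU/hospital stay comparison; read by default, an early death enters as a short stay

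*Combined protocol and SAP*

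**What the plan says.** The secondary objectives in section 2 include: "To evaluate ICU/hospital stay duration, clinical status and survival at discharge". Section 6 then lists "Duration of ICU/hospital stay duration" as a secondary endpoint and, as a separate item, "Mortality, readmission, clinical status and need for dialysis". Stay and death are thus both foreseen, but they are not linked.

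Stay is a quantitative variable, and no method is named for it specifically. It therefore falls under two general rules:

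- Section 7.1, summary of quantitative variables: "Described using minimum, maximum, mean, and standard deviation".
- Section 7.2, comparison: "Student's T-test, after verifying" normality and equal variances; then "If assumptions are violated: Mann-Whitney U test will be used".

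Section 7.6 sets complete-case analysis or "Multiple imputation considered" according to the share of missing data. Section 7.8 names the ITT and per-protocol populations. Neither section mentions deaths. The plan contains no time-to-event method, competing-event method, composite rank or days-alive-and-out-of-hospital measure.

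**The concern.** Length of stay is ended by two opposite events, going home and dying. A test on days alone cannot tell them apart. A patient who dies on day 2 has a two-day stay, and in a comparison where fewer days is better that counts in favour of the patient's arm.

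The patients have diabetes and acute coronary syndrome and are treated in an ICU, and mortality is an endpoint, so some deaths must be expected. With 71 patients, a small imbalance is enough to move the stay estimate. At stake is a secondary result that may point against the mortality result. A second risk is that, with no rule, the handling of deaths may be chosen after the data are seen. That matters more in a trial whose own section 9 acknowledges the lack of prospective registration and the resulting risk of reporting bias.

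**Working it through.** **Which reading the text leads to.** The document gives no figure for this endpoint to reproduce, so the first step is to set the rules side by side.

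1. A patient who dies in hospital has a known admission and a known end of stay. The value is recorded, so the missing-data rule in 7.6 is not triggered.
2. ITT (sections 3 and 7.8) points to keeping every randomised patient.
3. Section 7.2 applies to the variable as recorded.

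Together these enter an early death as a short stay. This is an inference from the defaults; the text does not state it.

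**Inputs for the illustration.** Only the 71 enrolled patients (sections 3 and 9) come from the document. The rest are assumptions:

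- 35 RIPC and 36 control patients.
- The same lognormal stay in both arms, median 8 days, log-SD 0.6.
- Deaths on days 1 to 3, mean day 2.
- In-hospital mortality of 3 to 8%, that is 0.03 × 71 = 2.1 to 0.08 × 71 = 5.7, or about 2 to 6 deaths.

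**Mean, SD and standard error of stay.**

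- Mean = 8 × exp(0.6²/2) = 9.58 days.
- SD = 9.58 × √(exp(0.36) − 1) = 6.3 days.
- SE of the mean difference = 6.3 × √(1/35 + 1/36) = 1.5 days.

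**Shift in the mean.** Each death replaces an average of 9.58 days by 2, a loss of 7.58 days. The expected difference, RIPC minus control, is 7.58 × (control deaths/36 − RIPC deaths/35).

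| Deaths control:RIPC | Calculation | Shift (days) | Simulated (two runs) |
|---|---|---|---|
| 2:2 | 7.58 × (0.0556 − 0.0571) | about 0 | about 0 (one run) |
| 2:0 | 7.58 × 0.0556 | 0.42 | 0.43, 0.44 |
| 4:1 | 7.58 × (0.1111 − 0.0286) | 0.63 | 0.64, 0.64 |
| 5:1 | 7.58 × (0.1389 − 0.0286) | 0.84 | 0.84, 0.90 |

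A positive value means that the arm with more deaths (here control) appears to have the shorter stay. Shifts of 0.6 to 0.9 day are about 0.4 to 0.6 of the 1.5-day SE.

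**Shift in the Mann-Whitney index** (probability that a RIPC patient stays longer than a control patient; 0.50 means no difference). Simulated values:

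| Deaths control:RIPC | Stay cut at death | Deaths ranked worst |
|---|---|---|
| 2:2 | 0.50 | 0.50 |
| 2:0 | 0.527–0.528 | 0.472–0.473 |
| 4:1 | 0.540 | 0.455–0.458 |
| 5:1 | 0.553–0.557 | 0.443–0.445 |

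The null SE of this index is √(72/(12 × 35 × 36)) = 0.069, so 0.540 to 0.557 lies about 0.6 to 0.8 SE from 0.50.

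**Effect on error rates.** A separate simulation used different assumptions: median 7 days, log-SD 0.6, exponential time to death with mean 2 days, and 36 v 35 patients. It gave these results with no true difference in stay:

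| Death rates | Apparent shortening (days) | t-test rejects | Mann-Whitney rejects |
|---|---|---|---|
| 5% v 5% | about 0 | 4.8% | 5.2% |
| 8% v 3% | 0.3 | 5.6% | 6.3% |
| 15% v 5% | 0.7 | 7.4% | 9.2% |
| 20% v 5% | 1.0 | 12.2% | 15.8% |

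Restricting to survivors rejected in about 5% of runs, but only because death was simulated as independent of how long the patient would have stayed.

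**The case against.** The strongest reply is that the plan is silent. A reader might infer that it counts in-hospital deaths as short stays. No section says so, and restricting the comparison to survivors is also compatible with the text. That stands, and it is why the bias is stated here as conditional. Silence does not remove the problem, though. Excluding deaths selects on an event after randomisation and departs from ITT, and leaving the matter open lets the choice follow the data.

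A reader might also infer from the index values that a few deaths reverse a true effect. They do not show that. The simulated arms have identical survivor stay, so there is no stay effect to reverse. The values below 0.50 come from a different estimand, one that combines death with stay.

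The reply on size also largely stands. Every input except 71 is assumed, balanced deaths cause no distortion, and within a plausible mortality range the shift is small against sampling error. Error rates rise clearly only at death-rate gaps of 10 to 15 points. Mortality is reported separately, so a contradiction with the stay result could be seen. Finally, worst-rank coding lets mortality drive a result called stay; that is a fair criticism unless the result is labelled for what it is.

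**Conclusion.** The point holds as a gap in a secondary analysis. The plan sends ICU/hospital stay to a t-test or Mann-Whitney test with no rule for in-hospital deaths. The default ITT reading lets early deaths shorten the apparent stay of the arm in which they occur.

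The consequence is modest. Under the stated assumptions the shift runs from about 0 (balanced deaths) to 0.6 to 0.9 day (4:1 to 5:1), under two-thirds of one standard error. The document reports no deaths by arm, so it does not support a claim that an imbalance occurred or that the stay result is in fact misleading. The primary CIN analysis is unaffected. This is a low-cost improvement, not a serious defect.

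**What to change.** In section 7.2, name a method for this endpoint. Analyse ICU stay and hospital stay as time to discharge alive, with in-hospital death as a competing event. Patients who die stay in the analysis as never discharged alive and are not censored at death. State the time origin, which the plan does not give.

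An alternative is a Mann-Whitney test with deaths given the worst rank. The two are not equivalent. The rank version should be labelled as a composite of death and stay.

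With either method:

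- report the number of deaths by arm beside the stay result;
- show stay among survivors as description only;
- disclose that the rule was added after data collection, which section 9 dates as complete in January 2017, with the available data already analysed.

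The cost is recoding of data already collected, with no new data needed. The downside is that the result is no longer a plain difference in mean days, and that as a post hoc rule it carries less weight than one fixed in advance.

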## 7. Statistical Analysis Plan (SAP)

### **7.1 Descriptive Statistics**

- **Qualitative variables:** Presented as frequencies and percentages per group/subgroup.
- **Quantitative variables:** Described using minimum, maximum, mean, and standard deviation.

## 7.2 Univariate Analysis

- **Qualitative comparisons:** Chi-square test.
- **Quantitative comparisons:** Student's T-test, after verifying:
  - **Normality:** Shapiro-Wilk test.
  - **Homogeneity of variances:** Levene test.
- If assumptions are violated: Mann-Whitney U test will be used.

## 7.3 Repeated Measures

- **Two-factor ANOVA with repeated measures** under General Linear Model (GLM).
- **Post hoc tests:** Bonferroni or Tukey, depending on variance structure.

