## 7.9 Software

- **SPSS Statistics v25.0** for Windows

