## 9. Study Limitations and Early Termination

Data collection was conducted over a three-years period. The final patient was enrolled and data collection for all primary and secondary outcomes, as well as adverse event monitoring, was completed in January 2017. Due to multiple logistical and operational constraints, no further patients were included after that date. Subsequently, with the emergence of the COVID-19 pandemic in December 2019, further recruitment was permanently halted. Additionally, preliminary analyses revealed that the primary outcome—the incidence of contrast-induced nephropathy (CIN) following remote ischemic preconditioning (RIPC)—did not show statistically significant differences between the intervention and control groups. These findings, combined with logistical constraints, led to the decision to halt the study before reaching the originally planned sample size. Thus, only 71 patients were enrolled—below the planned sample size. The reduced statistical power and lack of effect signal were key reasons for early termination.

**Note:** The study was not prospectively registered in a clinical trial database prior to patient enrollment. At the time of trial initiation, Spain did not have a clearly defined legal or regulatory framework mandating prospective registration for investigator-initiated interventional studies of this nature.

While Spain's Biomedical Research Law (Law 14/2007) established ethical principles and data protection standards, it did not impose a legal obligation to register non-pharmacological trials in platforms such as ClinicalTrials.gov or EudraCT. Furthermore, the regulatory provisions introduced by Royal Decree 1090/2015—which require prospective registration—apply specifically to clinical trials involving medicinal products and did not extend to procedural interventions such as remote ischemic preconditioning (RIPC). This regulatory gap, coupled with the academic nature of the study and its non-commercial scope, contributed to the lack of prospective registration.

This limitation is acknowledged and must be considered when interpreting results and assessing risk of reporting bias. The available data were analyzed and will be presented with full transparency regarding these limitations.

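### Adjusting HO-1 and MDA for their pre-procedure values would usually compare the arms more precisely than the planned repeated-measures ANOVA

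*Combined protocol and SAP*

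**What the plan says.** Section 7.3 of the SAP has two lines. The first names a "Two-factor ANOVA with repeated measures" under the general linear model. The second gives the post hoc tests as "Bonferroni or Tukey, depending on variance structure". The section does not name the markers, the sampling times or a baseline covariate.

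The link to particular markers is an inference. The Secondary Objectives ask for HO-1 and "malondialdehyde (MDA) before and after RIPC", and the Secondary Endpoints list "Plasma, urinary, and intracellular HO-1 levels" as well as MDA. Section 7.3 is the only part of the SAP that deals with repeated measurements, so arm and time are presumably its two factors.

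No other section adjusts the markers. Section 7.2 offers unadjusted two-group tests. The only covariate adjustment is the logistic model in section 7.4, which is "to predict CIN occurrence, adjusted for covariates".

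**The concern.** HO-1 and MDA carry the trial's evidence on mechanism, and only 71 patients were enrolled. When a pre-procedure value exists, regressing the post-procedure value on it removes the part of the between-patient variation that the baseline predicts. Subtracting the baseline fixes that regression slope at 1, which is usually not the best value. The confidence interval for the effect of RIPC on these markers is then wider than it needs to be, and a real effect is easier to miss. The cost is precision. Randomisation protects both analyses from bias.

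**Working it through.** **Inputs from the documents.** 71 patients enrolled in two arms (section 3); two-sided tests at 5% (section 7.10). The plan gives no SD, correlation, effect size or power for the markers, so it has no figure to reproduce.

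**Assumptions.** A 36/35 split; paired values in all 71 patients; one sample before and one after; post-procedure SD equal to 1; pre-post correlation rho of 0.3, 0.5 or 0.7; and, for power only, a true post-procedure difference of 0.5 SD.

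**Step 1: equal SDs.** The variance of the arm difference is (1/36 + 1/35) = 0.0563 times a factor:
- Arm-by-time test, the same as change scores: 2(1 − rho).
- ANCOVA on the pre-procedure value: 1 − rho².

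The ratio is 2(1 − rho)/(1 − rho²) = 2/(1 + rho). The number of patients that would give the same precision under ANCOVA is 71(1 + rho)/2.

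**Step 2: half-width and power.** The 95% half-width is the t quantile (about 1.995 on 69 or 68 degrees of freedom) times the standard error. At rho 0.5 this is 1.995 × √(1.00 × 0.0563) = 0.47 SD for arm-by-time and 1.995 × √(0.75 × 0.0563) = 0.41 SD for ANCOVA. Power by normal approximation is Φ(0.5/SE − 1.96).

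| rho | variance ratio | equivalent n of 71 | half-width, arm-by-time v ANCOVA (SD) | power, arm-by-time v ANCOVA |
|---|---|---|---|---|
| 0.3 | 1.54 | 46 | 0.56 v 0.45 | 43% v 60% |
| 0.5 | 1.33 | 53 | 0.47 v 0.41 | 56% v 68% |
| 0.7 | 1.18 | 60 | 0.37 v 0.34 | 78% v 84% |

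At rho 0.5, noncentral t gives 0.547 v 0.669, and simulation (20,000 runs) gives 0.540 v 0.658. With no true effect, both tests reject in about 5% of simulations (0.048 to 0.052), so both are valid.

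**Step 3: unequal SDs.** Let k be the post SD divided by the pre SD. The ratio becomes (1 + k² − 2·rho·k) / (k²(1 − rho²)). Numerator minus denominator is (1 − rho·k)², which cannot be negative, so the ratio is never below 1. It equals 1 where rho·k = 1. At rho 0.5:
- k = 0.75: 0.8125/0.4219 = 1.93
- k = 1: 1.33
- k = 1.5: 1.75/1.6875 = 1.04
- k = 2: 3/3 = 1.00, no gain

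With equal SDs at rho 0.9, the ratio is 2/1.9 = 1.05.

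**The case against.** The strongest reply is that the arm-by-time test already takes account of baseline by subtraction, so preferring ANCOVA is a choice of efficiency and not the repair of an error. That stands. A reader might infer that the ANOVA ignores baseline or gives a biased answer, and the documents do not support that.

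A reader might also infer that RIPC will be judged on the arm main effect. That effect averages in the pre-procedure value, halves the expected difference and has only 21% to 26% power under the same assumptions. Section 7.3 does not name its arm test, but nothing says the main effect was intended, so this is not a demonstrated loss. The missing contrast and the undefined post hoc rule are gaps in detail. By themselves they do not show a wrong analysis.

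The assumptions are also open to challenge. Planning post hoc tests fits three or more sampling times equally well. The figures above would not then describe the planned test, although baseline could still be used as a covariate. Not all 71 patients need have paired samples. The SD ratio and the correlation cannot be learned from the documents, and some plausible values leave almost no gain. These points limit the size of the benefit. They do not make ANCOVA less precise than change scores, beyond one degree of freedom.

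**Conclusion.** The point holds as a minor, low-cost improvement. With one sample before and one after, the planned arm-by-time comparison is valid but usually less precise than ANCOVA. Over the assumed correlations with equal SDs, its variance is 18% to 54% larger. At rho 0.5 the half-width would fall by 0.06 SD (0.47 to 0.41). The advantage shrinks towards nothing as rho times the SD ratio approaches 1. All these sizes rest on assumed inputs, and the application to HO-1 and MDA is inferred from the objectives. Only secondary markers are affected; the primary CIN comparison is unchanged.

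**What to change.** First state which markers were measured and when, and whether controls ("Hydration only") had a pre-procedure sample at the same point as the RIPC arm. If they did not, say so: neither the before/after ANOVA across arms nor the adjustment is then possible.

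If they did:
- Compare the arms on post-procedure HO-1 and MDA with the pre-procedure value as covariate. Use ANCOVA with one post-procedure sample, or a mixed model with baseline as covariate if there are more.
- Work on the log scale if the markers are skewed.
- Report the arm difference with a 95% CI.
- Apply the multiplicity correction of section 7.7 across markers and times, stating which of its two options is used.

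Section 9 says that "The available data were analyzed". The planned ANOVA should therefore be shown alongside on the same scale, with arm-by-time identified as its arm test, and the adjusted analysis should be labelled post hoc.

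The cost is a few lines of text and one degree of freedom per model with one post-procedure sample, in the software already named ("SPSS Statistics v25.0"), with no new data. The drawback is an analysis added with knowledge of the data in a trial that was not prospectively registered, which is why both results must be shown.
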